**Patient Education to Improve Pain Management in Older Adults with
Acute Musculoskeletal Pain: A Pilot Randomized Trial**

Protocol

**July 27, 2015
NCT02438384**

SCEENING / ED INTERVIEW

Participant Selection: To identify potential participants for this trial, monitor the ED Track Board in EPIC to find patients likely to be experiencing musculoskeletal pain. Eligibility criteria are listed below. Consult with [name] if you are unsure about a patient's potential eligibility.

- 50 years old or older
- Chief Complaint of musculoskeletal pain
- Can read and understand English
- Has a home phone or cell phone
- Score of ≥ 4 on Six Item Screener

Screening: Print out PDF copies of both the Screener and ED Interview. The other two tools will be used later and are not printed. The screener outlines the eligibility criteria. The last section of the Screener asks for verbal consent from the patient for enrollment in the trial. Completion of this form will determine whether or not the patient is eligible for and consenting to enrollment.

ED Interview: Ask all questions on this questionnaire and then follow the steps listed to randomize patients to treatment groups. Provide the brief explanation listed for the selected treatment group and show the BETTER Video to all patients selected for either "Video only" or "Video + Follow-up"

TABLET SETUP & USE

Two HP Stream 8 tablets are designated for use in this study. These tablets run the Windows 8.1 OS including full desktop capabilities. Information on important identification numbers for each of these tablets is available in the document titled BETTER Tablet Info. The tablets have already been set up specifically for use in this project.

Basic Setup: It is recommended that these tablets are setup with a local account rather than linked to someone's Microsoft account. Initially, a local account should be created with the username: BETTER and the password: better

1. Set the IE home page to UNC Better. Open the desktop and use Internet Explorer (IE) to navigate to <https://media.med.unc.edu/emergmed/better/index.html> Select the gear (options) icon in the top right corner and select "Internet Options." Under the General tab, tap "Use current" and then "Apply" on the bottom of the options box to set the new home page.
2. Create a desktop link to the BETTER site. Open IE and navigate to the UNC Better page (it should be the home page). Tap the gear icon in the top right corner and select "Add site to Apps." Tap the home button (Windows logo) and you are taken back to the start screen. Swipe up to view

all apps then press and hold the app labeled “UNC Better.” Select “Pin to Start” and this link will now be accessible from the start screen.

3. Unpin all other apps from the start screen. Press and hold over any app to edit. Select all apps except UNC Better and then tap “Unpin from Start” in the bottom left corner.
4. Put IE in full screen mode. From the UNC Better homepage, select the gear icon in the top right corner, tap File, and select Full screen.

Advanced Features: Along with the basic features listed above, these tablets have been customized for use in the BETTER project. All backgrounds and lock screens have been set to an image pulled from the video. The desktop has been cleared of all icons other than a link to the video and the taskbar is hidden. This helps to ensure that patients and providers do not accidentally alter the basic setup listed above. Because this setup does not use the traditional desktop display, a battery meter app has been installed on the start page. Lastly, these tablets have been set to NOT receive automatic updates. While we appreciate Microsoft’s dedication to providing almost a constant stream of updates for its devices, these tablets only experience a very specific type of use and are not likely to benefit from the vast majority of system updates.

Use:

- Turning the tablet on: Press and hold the small button on the side of the device.
- Turning the tablet off: You can either press and hold the small button on the side followed by swiping down, or swipe in from the right side of the screen, select “Settings,” then tap the Power icon and select Shut down.
- Logging in: After turning the tablet on, swipe up to reveal the Login screen. If correctly setup on the BETTER local account, the password will be “better”
- Connecting to Wi-Fi: To connect to a wireless network, swipe in from the right on any screen, select Settings, and then tap the Wi-Fi icon. You can select your network from here. “UNCH-Guest” is recommended.
- Volume control: The larger button on the side of the tablet is actually a two-way volume button.
- Opening the better video: From either the start screen or the desktop, select the UNC BETTER icon and you will be taken to the video website.
- Trouble shooting: All standard features (e.g. task manager, updates, system preferences) can be found with the search feature. To Search, swipe in from the right at any time and select “Search.” Have you tried turning it off and then back on?

RANDOMIZATION

Development of the Random Number Lists

Stratification: The two variables that we are adjusting distribution for in the BETTER Trial are gender and age (dichotomized into 50-64 years and 65 years or older). Age was selected as the primary variable

because of its association with short term knowledge gained from the video demonstrated in the BETTER video validation study.

Block Randomization: In each of the two random number lists, random distributed blocks of three and six will be used to ensure that screeners will not be able to guess the next study participant group assignment while still maintaining a high degree of even group distribution. A computer program developed by [name] was used to randomly assign numbers one through three in an even distribution into each block. This program works by randomly permuting the two lists 1,2,3 and 1,1,2,2,3,3 depending on the desired block size.

For a better understanding of the purpose of block randomization and blinding in small studies, refer to pages 156-159 in Designing Clinical Research

<https://books.google.com/books?id=7UWxJ5erSsC&q=157#v=snippet&q=157&f=false>

Random Number List: There are two random number lists used in this trial, one for each of the two age groups being assessed. Each list is created 21 numbers at a time and any list can be made again following the complete allocation of a block of six numbers.

Block Size Randomization: Blocks are randomized to contain either three or six numbers when each random number list (twenty-one numbers) is created.

Assignment of treatment group in the field

Master List The master list is actually two different random number lists, one for each strata of the distribution. These lists are randomized to block sizes and numbers are edited using the method described above to ensure equitable distribution. To keep the randomization process blinded, these lists should not be accessed by screeners who are actively enrolling patients.

Envelopes: Two sets of folded sticky notes labeled x01 through x21 are required for the blinded assignment of patients to treatment groups. Each card in one set is labeled "Younger" (101-121) corresponding to the 50-64 year old age group. Each card in the other set is labeled "Older" (201-221) corresponding to the 65 and older age group. Inside each folded sticky note is the corresponding number from that set's Random number list (i.e. envelope "Younger 101" has a piece of paper in it with the number that identifies the randomly assigned treatment arm for the first 50-64 year old enrolled in the study)

[figure not shown]
Assignment: This method requires that the screener carries the box containing both number lists (sticky note sets) with them when enrolling participants. After a prospective participant is deemed eligible, consents to participation in the trial, and completes the ED Interview, the screener will pull out the set of folded sticky notes that corresponds to the participant's age group. The next unopened sticky note in that category is opened and number of the treatment group found inside will determine which treatment group the participant will be assigned to.

Assignment – phone call alternative: This method requires a second research assistant that can be contacted by phone call. Following participant eligibility assessment, consent for participation in the trial, and the ED Interview, the screener calls the second research assistant to complete the randomized assignment. The person that is contacted by phone has the box containing both sets of sticky notes. Using the set that represents the participant's age group, the person on the phone will open the next sticky note to reveal the number of the treatment group that the participant will be assigned to. The phone call alternative will be used exclusively when multiple research assistants are screening participants at the same time.

RA FOLLOW-UP CALL

Phone calls are made to patients in the “video + follow-up” and “follow-up only” treatment arms. These calls must be made between 48 and 72 hours from patient enrolment. Refer to the REDcap data collection instrument titled “Follow-Up Call” to see the scripted introduction and questions that need to be asked to each patient. Using the answers given, evaluation of whether or not the patient will receive a phone call from [name] is made before terminating the call. The result of this decision is explained to the patient and a time-frame is set up for [name] to call the patient if it is deemed necessary. Before terminating the call, patients are asked about the status of any appointments that might have been scheduled with their primary care providers (PCP).

[figure not shown]
Study Physician Call Assessment: Based on the answers given patients in the “video + follow-up” and “follow-up only” treatment arms will be designated one of three status options, referred to here as Clear, Requesting, or Automatic. All patients assigned the “Clear” status meet the criteria answered “No” to all Assessment Survey questions and they either have no pain or they have pain in the 1-3 range but stated that they did not want to talk to a doctor when asked. Patients assigned the “Requested” status answered “No” to all Assessment Survey, have pain in the 1-3 range, and stated that they did what to talk to a doctor when asked. Patients assigned the “Automatic” status either had pain ≥ 4 and/or answered “Yes” to any of the survey questions (not include PCP appointment questions). Flow chart shown below.

STUDY PHYSICIAN CALL

If a patient assessed during the RA follow up call is designated to receive a call from the study physician, this call will be made either the same day as the RA call or the next day. This assures that the study physician call always happens within 4 days of the original ER visit. Ideally, the study physician call should be made using REDCap because of the information that is auto-filled from the RA call. The patient intervention flow chart for the study physician call is listed below.

The following protocol applies for patients in treatment arms “video + follow-up” and “follow-up only” who were assigned either the requested or automatic designation after RA follow-up call. Patients assigned the “Requested” status answered “No” to all Assessment Survey, have pain in the 1-3 range, and stated that they did what to talk to a doctor when asked. Patients assigned the “Automatic” status either had pain ≥ 4 and/or answered “Yes” to any of the survey questions (not include PCP appointment questions). Flow chart shown below.

Recommend follow up with primary care provider or UNC clinic for all patients not experiencing adequate pain relief.

UNC Family Medicine: [contact]
UNC Internal Medicine: [contact]
UNC Geriatrics: [contact]
UNC SCHC: [contact]

ONE MONTH EVALUATION

This evaluations requires an RA phone call and should be filled out in REDCap.

REDCap Analysis

Codes: In order to streamline the data analysis process, a series of rules was applied in the coding of answers choices in all redcap forms that will be analyzed. These codes are listed below.

x	This value is designated to answers that reflect that the question is Not Applicable. For example, the choice “No Prescription” for the question “Did you fill your prescription?”
0	This value is primarily designated to all minimum value answers (eg. No, None, Not at all, etc.) If used in a checkbox question, this value represents “Other”
1	If the question is yesno, then this value represents “Yes” If the question is a series, this number represents the next lowest value after “None” If the question is in a checklist or multiple choice, this value represents the first (top) choice
2-n	All other values are used for multiple choice questions and are listed numerically from top to bottom

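### By default the enrolling screener carries the current batch of assignments for both age strata on folded sticky notes, and the available text describes no seal, opacity or record of opening

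*Protocol*

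**What the plan says.** Under Envelopes in the Protocol's Randomization section: "Two sets of folded sticky notes labeled x01 through x21 are required for the blinded assignment of patients to treatment groups". One set (101 to 121) serves ages 50 to 64 and the other (201 to 221) serves ages 65 and over. The carrier is described as follows: "Inside each folded sticky note is the corresponding number from that set's Random number list". The same paragraph also calls the items cards, and its worked example is an envelope that "has a piece of paper in it with the number that identifies the randomly assigned treatment arm".

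Under Assignment: "This method requires that the screener carries the box containing both number lists (sticky note sets) with them when enrolling participants". The timing is stated: "After a prospective participant is deemed eligible, consents to participation in the trial, and completes the ED Interview", the screener takes out the set for that age group. Then: "The next unopened sticky note in that category is opened".

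There is a second method, in which another research assistant holds the box and is telephoned. Its use is limited: "The phone call alternative will be used exclusively when multiple research assistants are screening participants at the same time". The screener-held box is therefore the default.

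Under Block Randomization, blocks of three and six are mixed and are "used to ensure that screeners will not be able to guess the next study participant group assignment". Under Master List, screeners who are actively enrolling are kept away from the lists. Under Random Number List, each list is produced 21 numbers at a time.

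The opening section on screening addresses one reader, who watches the track board for likely patients, checks eligibility, obtains verbal consent, conducts the ED interview and then randomizes.

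**The concern.** Concealment means that whoever decides whom to approach, and how to present the trial, cannot know the next assignment. Here that person holds the next assignment on a piece of folded paper. Age is an eligibility item, so the relevant set is known before consent is sought.

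A screener who knew the next arm could approach or pass over a patient, wait for the next one, or describe the trial differently. The SAP adjusts the change in average pain for age, gender and baseline pain only. Selection on other factors related to pain at one month would remain in the three pairwise differences and their 95% confidence intervals.

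**Working it through.** The plan gives no figure on this point to reproduce. The check sets the relevant sections side by side.

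**1. What is in the box.** Two age sets of 21 notes give 2 × 21 = 42 when both are new, and fewer as notes are used. This is the current batch, not the whole trial, because lists are made 21 at a time. The count describes the stock carried. It does not measure bias, and it would be the same with sealed envelopes.

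**2. Who holds it.** Selection, consent, interview and randomization fall to one person in the screening section, and Assignment gives the box to the screener. The telephone method moves the box to someone else, but it applies only when several research assistants are screening. The text does not say that the person holding the box is then free of screening duties.

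**3. What the object is.** The heading says envelopes, the definition says folded sticky notes, one sentence says cards, and the example is an envelope containing paper. A reader cannot tell whether a note is the container or is placed in one. No version is described as sealed or opaque.

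**4. What could be detected afterwards.** Two kinds of departure behave differently.

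- *A note taken out of turn.* The notes are numbered and a master list exists. Follow-up calls are timed from enrolment, so enrolment times should be known. Comparing the order of enrolment with the order of the list could show a skipped or swapped note.
- *A note read ahead, refolded, then used in turn.* The order is intact, so that comparison shows nothing. The selection has already happened, in the choice of whom to approach or how.

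Mixed block sizes protect against guessing from past assignments. They give no protection for an assignment that has been read.

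**5. What each safeguard adds.** A seal and an opaque cover address reading ahead. Writing the participant's ID, date and time on the envelope before opening ties that participant to that assignment before it is known. A written time would not reveal reading ahead without a seal, so the two belong together.

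**The case against.** The strongest reply is that the point rests partly on silence, where the likeliest sources are unavailable. A figure in the part of the Protocol that describes the notes and their use is not shown. The ED Interview form, to which the screening section refers for the randomization steps, was not supplied either. Either could describe a seal or a log. This stands, and it is why the fix is conditional. It does not dispose of the point, because the text does state a carrier and a custodian, and a folded note held by the enroller is weak unless something further protects it.

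Second, the plan has real safeguards: numbered notes, opening in order after consent and interview, mixed blocks, and a withheld master list. The SAP also presents baseline characteristics by arm, which is a partial check on measured factors. These deserve credit, but they either depend on compliance or would miss reading ahead.

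Third, this is a pilot whose SAP plans estimates and intervals and describes no hypothesis test. That lowers the stakes. The estimates still rely on unbiased allocation.

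A reader might infer that the Protocol contradicts itself by barring screeners from the lists and then handing them both lists. The documents do not support that. The bar sits under Master List and reads naturally as covering the open list, while Assignment explains its own phrase as meaning the sets of notes. This is a matter of wording.

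**Conclusion.** The concern holds as a cheap improvement that should be made, not as a demonstrated failure. The default method gives the enrolling screener up to 21 assignments in each of two strata, on an object that can be read and refolded unnoticed, with no seal, opacity or opening record in the available text.

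Three stronger readings are tempting and unsupported:

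- *That concealment was broken or the results are biased.* Nothing shows a note opened or read out of turn, and the documents contain nothing from which a bias could be sized.
- *That the plan has no seal or log.* Only the available text lacks one.
- *That nothing could be checked later.* Skipped or swapped notes could be found in part from the master list; reading ahead could not.

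The conclusion assumes that the notes are used as described, folded and not enclosed in anything sealed. If the envelope wording is the accurate one and the envelopes are sealed and opaque, what remains is mainly inconsistent terminology and the lack of a described opening record.

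**What to change.** Unless already in place:

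- Put each assignment in a sealed, opaque, sequentially numbered envelope.
- After consent and the ED interview, and before opening, write the participant ID, date and time on the outside.
- Keep the opened envelopes, and have existing staff check them against the master list.
- Use one term for the object throughout the Envelopes and Assignment paragraphs.

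If the missing figure or the ED Interview form already describes a seal and a log, a sentence in the Protocol pointing to it is enough. If participants were already enrolled with notes, report how the notes were held and opened.

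The cost is one envelope per participant. At an assumed 1 minute per enrolment, a pair of sets takes 42 × 1 = 42 minutes; if the true time is double, 84 minutes. No new staff are needed. Custody stays with the screener, so the change reduces the risk without removing it.

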**Statistical Analysis Plan**

**NCT02438384**

**July 25, 2015**

Descriptive statistics will be used to present baseline characteristics for patients in each of the three study arms. To characterize the primary outcome by intervention arm, we will calculate point estimates along with 95% confidence intervals for change in average pain scores from baseline to one month with adjustments made for age, gender, and baseline pain scores. Pairwise difference in change in average pain between each of the three possible comparison pairs (video plus telecare vs. usual care, video alone vs. usual care, video plus telecare vs. video alone) will also be estimated along with 95% confidence intervals, adjusted for baseline pain, age and gender. Process outcomes will also be described using descriptive statistics.

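### The protocol and the SAP disagree on the third of three arms: a called follow-up-only arm in one, usual care in the other

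*Protocol*

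**What the plan says.** The protocol randomises to three group numbers. Under RANDOMIZATION, blocks are permutations of 1,2,3 or of 1,1,2,2,3,3, and the folded note opened at enrolment carries only a number. The arm names appear elsewhere. The ED Interview paragraph names two arms that are shown the video: *video only* and *video + follow-up*. The call sections name a third, *follow-up only*, and give it three instructions:

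- RA FOLLOW-UP CALL: "Phone calls are made to patients in the “video + follow-up” and “follow-up only” treatment arms".
- Study Physician Call Assessment: "patients in the “video + follow-up” and “follow-up only” treatment arms will be designated one of three status options".
- STUDY PHYSICIAN CALL: "The following protocol applies for patients in treatment arms “video + follow-up” and “follow-up only", for those whose status triggers that call.

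On timing, the protocol says of the research assistant (RA) calls "These calls must be made between 48 and 72 hours from patient enrolment" and of the physician call "This assures that the study physician call always happens within 4 days of the original ER visit".

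The SAP also has three arms: "Descriptive statistics will be used to present baseline characteristics for patients in each of the three study arms". Its primary analysis gives "point estimates along with 95% confidence intervals for change in average pain scores from baseline to one month" by arm, then pairwise differences for "video plus telecare vs. usual care, video alone vs. usual care, video plus telecare vs. video alone". It has no arm that receives calls without the video.

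**The concern.** The two documents agree on the number of arms and, if telecare means the follow-up calls, on two of them. They differ on the third, and the difference goes beyond naming. As written, the follow-up-only arm gets a scripted early call and triage to a study physician, on the same terms as the video-plus-follow-up arm. Usual care in the SAP is the comparator for two of the three pairwise differences.

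What is at stake is what those two differences mean. Against a usual-care arm, they estimate the effect of the video with calls, and of the video alone, over no study intervention. Against a called arm, the first estimates what the video adds to calls, and the second sets the video against calls. These are different questions, and results from one design cannot be reported under the labels of the other.

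**Working it through.** No figure in the plan needs reproducing. The check sets the arm labels side by side and counts.

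**1. Arms by document**

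| | Protocol | SAP |
|---|---|---|
| Number of arms | 3 (codes 1, 2, 3) | 3 (stated) |
| Video and calls | video + follow-up | video plus telecare |
| Video, no calls | video only | video alone |
| Third arm | follow-up only (called) | usual care |

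The match in the second row assumes that telecare means the follow-up calls. If it meant something else, the documents would disagree on more than one arm.

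**2. Could both third arms exist?** That would make four arms. Four arms give C(4,2) = 6 pairs and three give C(3,2) = 3. The SAP treats its three pairs as all the possible ones, and the protocol permutes only three codes. A four-arm reading is therefore ruled out.

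**3. Do the calls come before the outcome?** The RA call is due by 72 hours, which is 3 days. The physician call follows the same day or the next, so 3 + 1 = 4 days at most, in line with the protocol's own limit. The primary outcome is taken at one month. Any call to the third arm therefore falls between baseline and outcome.

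**4. Planned primary estimates that involve the third arm**

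- Planned: 3 arm-specific changes + 3 pairwise differences = 6.
- Involving the third arm: 1 arm-specific change + 2 pairwise differences = 3.
- Not involving it: the changes in the two video arms and the difference between them = 3.

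**5. What follows under each design**

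- *The third code is follow-up only.* Its participants are called, and the 3 estimates in step 4 do not describe usual care or a comparison with it.
- *The third code is usual care.* The SAP's contrasts are complete, and the labels in the call sections are wrong. If staff took the label to mean the third arm, they could call controls. If no participant carries the label, the instruction may reach nobody and change no estimate.

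Choosing between these needs the key from code to arm. The visible text has none. The arm explanations are on the ED Interview form, which is not reproduced.

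**The case against.** The strongest reply is that the answer may lie in material that cannot be seen: the ED Interview form, the flow charts, or the removed part at the start of the SAP file. If the form labels the third code as usual care, following the call sections literally means calling only the video-plus-follow-up arm. The stray label then harms no one. This stands, and it limits what may be claimed about consequences. It does not remove the conflict, because the unseen material could show which design is intended but could not make the call sections agree with the SAP.

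A second reply is that follow-up only might mean outcome follow-up only, which would be usual care under another name. This does not fit the text. The one-month evaluation is a separate section with its own call, while the early call and the physician triage are attached to the follow-up-only label.

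A reader might also infer three stronger things that the documents do not support:

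- *That controls were, or certainly would be, called.* This depends on how the third code is labelled where staff look it up.
- *That usual care is not part of the design because the visible protocol never names it.* An arm with no video and no calls need not appear in sections about videos and calls.
- *That three uses of the label rule out a slip.* The physician-call section repeats the status definitions of the assessment section, including the same typing error. Text was copied between them, so the uses are not independent.

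Finally, this is a pilot that plans estimates with intervals and states no tests. That lowers the stakes, but an estimate still needs a defined comparator.

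**Conclusion.** The contradiction is real and lies in the visible text: the third of three arms is follow-up only in the protocol's call sections and usual care in the SAP. The wording of at least one document has to change. The disputed arm enters 3 of the 6 planned primary estimates. The comparison of video plus telecare with video alone is unaffected.

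The conclusion rests on reading telecare as the follow-up calls, and on the three-arm count that both documents give. It does not say which design is intended or which was carried out. The SAP is dated two days before the protocol (July 25 and July 27, 2015), and no visible text describes a change of arms. The point must be settled because the comparator of two primary contrasts is undefined, not because contamination of a control group has been shown.

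**What to change.** Reconcile the passages so that both documents carry one list of three arms. For each arm, give the randomisation code and the study components it receives: video, RA call, physician call. Then align the RA call, status assessment and physician call sections, and the SAP's contrasts, to that list.

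- If the third arm is usual care, correct the follow-up-only labels in the protocol's call sections.
- If it is follow-up only, restate the two usual-care contrasts in the SAP so that they name the comparator actually used.

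The sponsor has to say which applies. The cost is wording in one or both documents, with no extra patients or procedures.
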